6.3.3 Study Day 0: Baseline Evaluation and Randomization

6.3.3.1 Baseline Clinical Data

- Clinical data must be collected just prior to randomization (no more than 4 hours between collection and randomization).
- Vital signs, including SpO₂. These values may be obtained from clinically collected information if they were obtained within 4 hours prior to randomization. Vital signs should be collected in a complete set within 30 minutes of each other.
 - This can be the same set of vital signs as used at screening as long as they were obtained within 4 hours prior to randomization.
- Clinical data:
 - Assessment of clinical status (6-point ordinal scale)
 - Glasgow coma scale
 - Early warning score
 - NEW score for age \geq 18 years
 - PEW score for age $<$ 18 years
 - Organ dysfunction score
 - SOFA score for age \geq 18 years
 - PELOD score for age $<$ 18 years
 - Measures of clinical support:
 - Hospitalization
 - Oxygen requirement
 - Mechanical ventilator requirement
 - ICU requirement
 - ECMO requirement
 - Chest x-ray finding if performed for clinical indication within 24 hours prior to randomization
- Assessment of ARDS using PaO₂ (or SpO₂), FiO₂, and recent chest x-ray data.

- Note: If the above-listed clinical data assessments were performed for screening and collected < 4 hours prior to randomization, they do not need to be repeated for baseline assessment unless the investigator believes there has been a likely change in the score based on clinical assessment.
- Review new medical conditions, concomitant medication, and evaluate for AEs that have occurred after informed consent.

6.3.3.2 Baseline Clinical Safety Laboratory Tests

Blood draws for the following laboratory tests will be performed prior to randomization and plasma administration. The results do not need to be available prior to randomization or plasma administration.

- CBC with differential white cell count (to include neutrophil and lymphocyte percentages), hemoglobin, hematocrit, and platelets
- Blood chemistries (creatinine, glucose, total protein, ALT/GPT, AST/GOT, total bilirubin)
- PT/INR

Any tests not collected clinically, should be obtained according to the protocol. Results from laboratory tests performed for clinical indications < 12 hours before randomization may be used if available.

6.3.3.2.1 Pediatric Blood Collection Guidelines

Refer to institutional policies and recommendations on safe blood sample volume limits for pediatric patients. Sites may reduce the volume of research blood sample collection in order to remain within these limits.

6.3.3.3 Baseline Research Procedures on Day 0

The following baseline research procedures will be performed after screening evaluations and determination of eligibility have been completed but prior to randomization and plasma administration. These must be performed just prior to randomization (no more than 4 hours between collection and randomization). Baseline research samples should not be collected for screen failures.

- OP (throat) swab for quantitative PCR
- 25.5 mL of blood for adults or 8.5 mL of blood for children should be obtained. This will be used for the following laboratory tests:
 - HAI to influenza A/H1N1 and A/H3N2
 - Stored samples for other research tests evaluating the immune response to influenza as defined in Section [7.5](#)

6.3.3.4 Randomization

Those subjects found eligible for randomization in this study will be randomized in the IWRS system as noted in Section [5.2](#), after baseline assessments have been completed.

6.3.4 Study Plasma Administration

After all baseline evaluations and randomization have been completed, subjects will receive the study plasma. Refer to Section [5.7](#) for dosing information. The calendar date and 24-hour clock time for study plasma administration should be recorded for the start and end of each infusion.

Vital signs should be obtained during plasma infusion according to institutional policies. Vital signs during infusion are not collected in the database. All grade 3 or grade 4 AEs (e.g. hypotension) or other events (chest pain, rash, etc.) and all SAEs occurring during study plasma administration should be captured as noted in Section [10.2](#).

6.3.5 Study Day 1

Day 1 is always the calendar day following the day of randomization, even if the plasma infusion starts late in the day of randomization or if the plasma infusion starts on the calendar day following the day of randomization. However, plasma administration should be completed prior to collecting the Day 1 visit procedures.

6.3.5.1 Clinical Data on Day 1

- Vital signs, including SpO₂. These values may be obtained from clinically collected information if they were obtained within 4 hours of the study assessment. Vital signs must be collected in a complete set within 30 minutes of each other.
- Clinical data
 - Assessment of clinical status (6-point ordinal scale)
 - Glasgow coma scale
 - Organ dysfunction score
 - SOFA score for age \geq 18 years
 - PELOD score for age $<$ 18 years
 - Measures of clinical support:
 - Hospitalization
 - Oxygen requirement
 - Mechanical ventilator requirement
 - ICU requirement
 - ECMO requirement
 - Chest x-ray finding if performed for clinical indication
 - Assessment of ARDS using PaO₂ (or SpO₂), FiO₂, and recent chest x-ray data.
- Review new medical conditions, concomitant medication, and evaluate for AEs

6.3.5.2 Clinical Laboratory Tests on Day 1

The following laboratory test will be performed:

- CBC with differential white cell count (to include neutrophil and lymphocyte percentages), hemoglobin, hematocrit, and platelets
- Blood chemistries (creatinine, glucose, total protein, ALT/GPT, AST/GOT, total bilirubin)
- PT/INR

Results from laboratory tests performed for clinical indications $<$ 12 hours before the visit may be used if available. Any tests not collected clinically, should be obtained according to the protocol.

6.3.5.3 Research Procedures on Day 1

The following research procedures will be performed:

- 17 mL of blood for adults or 8.5 mL for children should be obtained. This will be used for the following laboratory tests:
 - HAI to influenza A/H1N1 and A/H3N2
 - Stored samples for other research tests evaluating the immune response to influenza as defined in Section 7.5

6.3.6 Study Day 2

If the subject is no longer hospitalized, this visit may occur by telephone. In this case, the assessments below should be restricted to the ordinal scale, oxygen requirements, new medical conditions, concomitant medication, and evaluation for AEs.

6.3.6.1 Clinical Data on Day 2

- Vital signs, including SpO₂. These values may be obtained from clinically collected information if they were obtained within 4 hours of the study assessment. Vital signs must be collected in a complete set within 30 minutes of each other.
- Clinical data
 - Assessment of clinical status (6-point ordinal scale)
 - Measures of clinical support:
 - Hospitalization
 - Oxygen requirement
 - Mechanical ventilator requirement
 - ICU requirement
 - ECMO requirement
 - Chest X-ray finding if performed for clinical indication
 - Assessment of ARDS using PaO₂ (or SpO₂), FiO₂, and recent chest x-ray data.
 - Review new medical conditions, concomitant medication, and evaluate for AEs

6.3.7 Study Day 3

The subject's ability to provide consent should be evaluated. Any subject who was unable to previously provide consent independently should be administered the informed consent according to institutional policies.

6.3.7.1 Clinical Data on Day 3

This visit must occur in the hospital or clinic, or be conducted as a home visit if authorized in accordance with Section 6.2. During this visit the following will occur:

- Vital signs, including SpO₂. These values may be obtained from clinically collected information if they were obtained within 4 hours of the study assessment. Vital signs should be collected in a complete set within 30 minutes of each other.
- Clinical data
 - Assessment of clinical status (6-point ordinal scale)
 - Glasgow coma scale
 - Early warning score
 - NEW score for age \geq 18 years
 - PEW score for age $<$ 18 years
 - Organ dysfunction score
 - SOFA score for age \geq 18 years
 - PELOD score for age $<$ 18 years
 - Measures of clinical support:
 - Hospitalization
 - Oxygen requirement
 - Mechanical ventilator requirement
 - ICU requirement
 - ECMO requirement
 - Chest x-ray finding if performed for clinical indication
 - Assessment of ARDS using PaO₂ (or SpO₂), FiO₂, and recent chest x-ray data.
- Review new medical conditions, concomitant medication, and evaluate for AEs

6.3.7.2 Clinical Safety Laboratory Tests on Day 3

The following laboratory test will be performed:

- CBC with differential white cell count (to include neutrophil and lymphocyte percentages), hemoglobin, hematocrit, and platelets
- Blood chemistries (creatinine, glucose, total protein, ALT/GPT, AST/GOT, total bilirubin)
- PT/INR

Results from laboratory tests performed for clinical indications < 12 hours before the visit may be used if available. Any tests not collected clinically, should be obtained according to the protocol.

6.3.7.3 Research Procedures on Day 3

The following research procedures will be performed:

- OP (throat) swab for quantitative PCR
- 17 mL of blood for adults or 8.5 mL for children should be obtained. This will be used for the following laboratory tests:
 - HAI to influenza A/H1N1 and A/H3N2
 - Stored samples for other research tests evaluating the immune response to influenza as defined in Section [7.5](#)

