5.9 Study Plasma Administration

Study plasma should be administered as soon as possible. The plasma should be started no later than 12 hours after randomization for units that are available at a site, and no later than 24 hours for units that are shipped from the repository for that subject. The plasma infusion rate will be determined by the individual sites based on institutional policy.

Before administration of study plasma, the investigator (or designated study staff) must verify the plasma label(s) to confirm that the DIN(s) on the plasma unit(s) match the IWRS randomization notification email for the subject, as well as to confirm the appropriate dose to be administered (refer to Section 5.7). Plasma DIN(s) and plasma product code(s) should be recorded in source documents at the time of infusion along with the volume administered.

The calendar date and 24-hour clock time for study plasma administration should be recorded for the start and end of each infusion. The intervals between units may occur per a site's blood establishment SOPs and/or normal practice. Pretreatment to minimize transfusion reactions (e.g. acetaminophen, diphenhydramine, etc.) according to local institutional policies are permitted in this study, but any such medications should be captured as concomitant medications.

If an AE develops during infusion, the infusion may be slowed temporarily or permanently discontinued, as deemed appropriate by the investigator. As a guide, local side effects (e.g., infusion site burning) or non-allergic systemic effects (e.g., chills) can generally be alleviated by slowing the rate of infusion, whereas allergic side effects (e.g., rash, wheezing, hypotension) should result in the cessation of study plasma infusion. All grade 3 or grade 4 AEs, and all SAEs occurring during study plasma administration should be captured as noted in Section 10.2. Additionally, any AEs resulting in plasma discontinuation (regardless of AE grade) should be recorded.

The investigator is ultimately responsible for making the decision to slow or stop study plasma infusion. If the infusion is discontinued, the subject should be treated according to best available local practices and procedures, and the Medical Monitor should be notified. Reason(s) for premature discontinuation of any plasma infusion must be documented in the medical record (source document) and on the eCRF.

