#### **8.4 Changes in laboratory test values and vital signs**

The protocol requires the collection of the following at Days 0, 1, 3 and 7:

- CBC: White cell count and differential white cell count (neutrophil and lymphocyte percentages), hemoglobin, hematocrit, and platelets.
- Blood chemistries: creatinine, glucose, total protein, ALT/GPT, AST/GOT, total bilirubin.
- Vital signs, including SaO2.
- PT, INR.

- a. Figure and associated Table: For each test: median, 25th and 75th percentiles at each required measurement time (min, max and sample size also in table).
- b. Figure and associated Table: For each test: median, 25th and 75th percentiles change from Day 0 at each required measurement time (min, max and sample size also in table).

Note –laboratory abnormalities that are clinically significant, or require an intervention, are captured as AEs above.

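### The 12-hour look-back for Day 1 safety laboratories does not require the sample to follow the study plasma, so a compliant Day 1 value can predate the end, or even the start, of the infusion

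*Protocol*

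**What the plan says.** Protocol 6.3.5 fixes the calendar: "Day 1 is always the calendar day following the day of randomization", even when plasma starts late on Day 0 or not until the next day. It also sets an order: "plasma administration should be completed prior to collecting the Day 1 visit procedures".

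Protocol 6.3.5.2 lists the Day 1 blood count, chemistries and PT/INR. For tests done on clinical grounds, results from less than "12 hours before the visit may be used if available"; only tests not available that way must be drawn for the study.

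Protocol 5.9 sets the latest plasma start. For on-site stock the rule reads: "The plasma should be started no later than 12 hours after randomization for units that are available at a site". Where plasma has to be sent in for a subject, the limit is instead 24 hours.

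For baseline, Protocol 6.3.3.2 says "Blood draws for the following laboratory tests will be performed prior to randomization and plasma administration". It has its own allowance for clinical results from less than "12 hours before randomization may be used if available".

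SAP 8.4 summarizes each test by median and quartiles (with minimum and maximum), both as a value and as "change from Day 0 at each required measurement time", for Days 0, 1, 3 and 7. SAP Section 3 assigns data to visits by days since randomization and, where several values fall in a window, takes the one nearest the scheduled time.

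**The concern.** The ordering sentence in 6.3.5 shows that Day 1 is meant to be a post-infusion assessment. The look-back in 6.3.5.2 is anchored to the visit and not to the plasma, so it can reach back past the infusion that the visit was timed to follow. Nothing in 6.3.5.2, in the general chart-data rule of Protocol 6.2, or in SAP Section 3 or 8.4 asks whether a sample was drawn after the plasma.

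Two things are at stake. Some values in the Day 1 column of the laboratory tables may come from subjects who had not yet received plasma, or had received only part of it. And once a pre-infusion chart result has met the Day 1 requirement, the protocol no longer asks for a post-infusion safety draw until Day 3.

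**Working it through.** The plan states no figure to reproduce; the check is clock arithmetic on its own timing rules.

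**Inputs.** Look-back of 12 h before the visit (Protocol 6.3.5.2). Latest plasma start 12 h or 24 h after randomization (5.9). Day 1 is the next calendar day, with plasma complete before its procedures (6.3.5). Visits preferably before noon (6.1); first assessment at about 08:00, stated for the ordinal scale (7.3.1). The individual clock times below are assumptions chosen to satisfy these rules.

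**Formulas.** Let R be randomization, S and E the start and end of plasma, and V the visit, with R ≤ S ≤ E ≤ V. The look-back runs from V − 12 h to V. When S falls inside it:
- hours before plasma start = S − (V − 12 h)
- hours during infusion = E − S
- hours after infusion = V − E

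**Results** (D0 and D1 are Day 0 and Day 1):

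| Timeline | R | Plasma | S − R | V | Look-back opens | Before start | During | After |
|---|---|---|---|---|---|---|---|---|
| 1, on-site | 21:00 D0 | 01:00–05:00 D1 | 4 h | 08:00 D1 | 20:00 D0 | 5 h | 4 h | 3 h |
| 2, on-site | 22:00 D0 | 23:00 D0–02:00 D1 | 1 h | 08:00 D1 | 20:00 D0 | 3 h | 3 h | 6 h |
| 3, on-site | 14:00 D0 | 01:30–05:30 D1 | 11.5 h | 08:00 D1 | 20:00 D0 | 5.5 h | 4 h | 2.5 h |
| 4, on-site | 20:00 D0 | 06:00–10:00 D1 | 10 h | 11:00 D1 | 23:00 D0 | 7 h | 4 h | 1 h |
| 5, shipped | 16:00 D0 | 14:00–18:00 D1 | 22 h | 19:00 D1 | 07:00 D1 | 7 h | 4 h | 1 h |

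No timeline involves a deviation. In timeline 4, 6 of the 7 pre-infusion hours (00:00 to 06:00) are dated Day 1; in timeline 5 all 7 are. Those draws pass a rule based on sample date as well as one based on visit date.

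**Reuse of a baseline draw.** A baseline sample drawn at time B qualifies as Day 1 only if it was a clinical draw and B > V − 12 h. Because B falls on Day 0, this needs a visit before noon. In timeline 2, a clinical draw at 21:30 is 10.5 h before the visit and qualifies under both allowances; used twice, it gives a change of exactly zero.

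**Reach under assumed timings.** Assume randomization uniform from 08:00 to 24:00; plasma start uniform from 0.5 h to a maximum of 4, 12 or 24 h later; infusion lasting 2, 4 or 6 h; and a visit at 08:00, 10:00 or 12:00, or at the end of infusion if that is later. The look-back then extends before plasma start for about 14% to 82% of subjects. It reaches a baseline draw taken at randomization for 0% to 25%, and one taken 4 h earlier for about 0%. These are the shares for whom the rule permits such a value, not the shares who would have one.

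**After the fix.** The admissible window becomes max(V − 12 h, E) to V, which is 3, 6, 2.5, 1 and 1 h in the five timelines. No part of it precedes the end of infusion.

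**The case against.** The best defence is that 6.3.5 governs 6.3.5.2: laboratories are Day 1 procedures, so a sensible site would apply the ordering sentence to chart results too. That is probably the intent. But the sentence controls when procedures are collected, while the look-back controls how old a chart result may be, and a site reading both literally breaks neither.

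The defence is also right that the stakes are limited. SAP 8.4 is descriptive with no test, both arms receive plasma, Days 3 and 7 are sampled, and laboratory abnormalities of Grade 3 or higher are recorded as adverse events (Protocol 10.2).

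A reader might infer four stronger claims that the documents do not support:
- *The baseline tube will routinely serve as Day 1.* It must be a clinical draw, with evening randomization and a morning visit. It would also be excluded if the SAP windows are applied to sample date, which the SAP does not state either way.
- *Nine of the 12 hours in timeline 1 precede the plasma.* Five do; the other four fall during the infusion.
- *The Day 1 change shrinks in proportion to the fraction of pre-infusion values.* SAP 8.4 reports medians, which need not shrink in proportion. A pre-infusion draw distinct from baseline can still show change from the illness or other care. The fraction itself is unknown.
- *The safety comparison in Protocol 7.4 is undermined.* That section concerns adverse event rates, and the safety objectives in 2.2 are Grade 3 and 4 events and SAEs.

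**Conclusion.** The gap is real and modest. As written, 6.3.5.2 lets a clinical draw taken before or during the infusion stand as the Day 1 laboratory value without any deviation. SAP Sections 3 and 8.4 do not remove such a value, at least when it is dated Day 1. In the compliant timelines above, 3 to 7 of the 12 look-back hours precede plasma start.

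The consequence is confined to the descriptive Day 1 laboratory values and their change from Day 0, and to a possible delay of the first scheduled post-infusion laboratory check to Day 3. How many values would be affected cannot be estimated, because the documents give no distribution of draw, infusion or visit times. The primary endpoint, clinical status at Day 7, does not use these laboratories.

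**What to change.** In Protocol 6.3.5.2, add to the look-back sentence: 'provided the sample was drawn after the end of the last study plasma infusion; otherwise obtain it at the visit'.

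In SAP 8.4, state that the windows apply to sample date and time, and that a value drawn before the recorded end of infusion is not counted as a Day 1 value.

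The cost is small. Infusion start and end times are already recorded (Protocol 5.9 and 6.3.4), and research blood is already drawn at the Day 1 visit (6.3.5.3), so some subjects would have safety tubes added to that draw. The documents do not show that laboratory draw times are captured; if they are not, a data field must be added.

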6.3.8 Study Day 7 (± 1)

The subject's ability to provide consent should be evaluated. Any subject who was unable to previously provide consent independently should be administered the informed consent according to institutional policies.

6.3.8.1 Clinical Data on Day 7

This visit must occur in the hospital or clinic, or be conducted as a home visit if authorized in accordance with Section [6.2](#). During this visit the following will occur:

- Vital signs, including SpO₂. These values may be obtained from clinically collected information if they were obtained within 4 hours of the study assessment. Vital signs should be collected in a complete set within 30 minutes of each other.
- Concomitant medications
- Clinical data
 - Assessment of clinical status (6-point ordinal scale)
 - Glasgow coma scale
 - Early warning score
 - NEW score for age ≥ 18 years
 - PEW score for age < 18 years
 - Organ dysfunction score
 - SOFA score for age ≥ 18 years
 - PELOD score for age < 18 years
 - Measures of clinical support:
 - Hospitalization
 - Oxygen requirement
 - Mechanical ventilator requirement
 - ICU requirement
 - ECMO requirement
 - Chest x-ray finding if performed for clinical indication
 - Assessment of ARDS using PaO₂ (or SpO₂), FiO₂, and recent chest x-ray data.

- Review new medical conditions, concomitant medication, and evaluate for AEs

6.3.8.2 Clinical Safety Laboratory Tests on Day 7

The following laboratory test will be performed:

- CBC with differential white cell count (to include neutrophil and lymphocyte percentages), hemoglobin, hematocrit, and platelets
- Blood chemistries (creatinine, glucose, total protein, ALT/GPT, AST/GOT, total bilirubin)
- PT/INR

Results from laboratory tests performed for clinical indications < 24 hours before the visit may be used if available. Any tests not collected clinically, should be obtained according to the protocol.

6.3.8.3 Research Procedures on Day 7

The following research procedures will be performed:

- 17 mL of blood for adults or 8.5 mL for children should be obtained. This will be used for the following laboratory tests:
 - HAI to influenza A/H1N1 and A/H3N2
 - Stored samples for other research tests evaluating the immune response to influenza as defined in Section [7.5](#)

6.3.8.4 Day 7 Clinical Status

If the Day 7 visit does not occur, in person, attempts should be made to call the subject to obtain information about their disposition and functional status (in order to score the Day 7 Clinical Status [primary endpoint]). If the subject cannot be reached by phone, the hospital record should be reviewed to determine if/when the subject was discharged, and to determine the clinical status on Day 7. This missed visit may still be a protocol deviation, but this would allow the primary endpoint to be ascertained.

6.3.9 Study Day 14 (± 2)

If the subject is no longer hospitalized, this visit may occur by telephone. In this case, the assessments below should be restricted to the ordinal scale, oxygen requirements, new medical conditions, concomitant medication, and evaluation for AEs. The subject's ability to provide consent should be evaluated. Any subject who was unable to previously provide consent independently should be administered the informed consent according to institutional policies.

6.3.9.1 Clinical Data on Day 14

- Vital signs, including SpO₂. These values may be obtained from clinically collected information if they were obtained within 4 hours of the study assessment. Vital signs should be collected in a complete set within 30 minutes of each other.
- Clinical data
 - Assessment of clinical status (6-point ordinal scale)
 - Measures of clinical support:
 - Hospitalization
 - Oxygen requirement
 - Mechanical ventilator requirement
 - ICU requirement
 - ECMO requirement
 - Assessment of ARDS using PaO₂ (or SpO₂), FiO₂, and recent chest x-ray data.
- Review new medical conditions, concomitant medication, and evaluate for AEs

